- 5. Medical history (name of disease or syndrome (diagnosis], classification of history or concurrent disease..)
 - * History: Chronic disease (including allergy), disease requiring treatment, disease or disorder with surgery, hospitalization or sequelae, and other relevant disease or syndrome that are cured before commencement of XELJANZ treatment (no treatment and no symptoms)
 - * Concurrent disease: Chronic disease (including allergy), disease requiring treatment disease or disorder with surgery, hospitalization or sequelae, and other relevant disease or syndrome that require any treatment or require no treatment but have residual symptoms at the time of commencement of XELJANZ treatment

6. Prior treatment for ulcerative colitis

The status of prior treatment (drug and non-drug therapy) for the last episode before commencement of XELJANZ treatment (an episode treated with XELJANZ) should be recorded.

For biological products, the status of use throughout the past treatment of ulcerative colitis should be recorded, and if any biological product was used, the name of the product and the classification of primary failure or secondary failure• should be recorded.

*: Primary failure: Lack of effectiveness or insufficient effectiveness with treatment for an appropriate period at the approved dosage and administration

Secondary failure: Loss of effectiveness (relapse) with continued treatment after achieving a clinical response (remission) with treatment for an appropriate period at the approved dosage and administration

Indeterminate: Treatment is discontinued due to any reason other than "not effective" (e.g., adverse events) and determination whether it is primary failure or secondary failure cannot be made

- 7. Smoking history (status of smoking at the start of the investigation)
- 8. Family history of malignant tumor (including lymphoma)

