7.3.4. Concomitant therapy for ulcerative colitis

7.3.4.1. Drug therapy

The record of treatments• for ulcerative colitis used from the date of commencement of XELJANZ treatment to the date of completion of the observation period (or date of XELJANZ discontinuation) should include the following information.

- 1. Drug name
- 2. Route of administration
- 3. Dosage form (topical agents only)
- 4. Duration of treatment
 - *: 5-ASAs (oral, enema, suppository), steroids (oral, enema, suppository, injection), immunomodulators (oral, injection), biological products (injection)

7.3.4.2.Non-drug therapy

The record of non-drug treatments given from the date of commencement of XELJANZ treatment to the date of completion of the observation period (or date of XELJANZ discontinuation) should include the following information.

- 1. Name of the therapy
- 2. Period of administration
- 3. Reason for the administration of non-drug therapy

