7.3.5. Status of vaccination

The record of vaccines given in relation to the treatment of ulcerative colitis should include the following information from baseline to the date of completion of the observation period (or date of XELJANZ discontinuation).

- 1. Herpes zoster vaccine: Status and date of vaccination, drug name (vaccine name)
- 2. Pneumococcal vaccine: Status and date of vaccination

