Using the SAS and EAS, a breakdown of patients by each of the following factors will be presented in terms of n and proportion. Concomitant medications and non-drug therapies will be defined in align with the data collection period for adverse reactions and AEs so that relationship to adverse reactions and AEs can be assessed.

- Concomitant medications (drugs recorded in the CRF entry "Drug therapies for UC prior treatment and concomitant therapies" that were used in the period from the start of the treatment with this drug to the discontinuation of treatment or 60 weeks after the start of treatment, whichever came first)
- Non-drug therapies (non-drug therapies recorded in the CRF entry "Non-drug therapies for UC prior treatment and concomitant therapies" that were used in the period from the start of the treatment with this drug to the discontinuation of treatment or 60 weeks after the start of treatment, whichever came first)
- Prior medications (medications recorded in the CRF entry "Past history of treatment for UC biological therapeutics", and medications recorded in the CRF entry "Drug therapies for UC prior treatment and concomitant therapies" of which administration had been started by the day before the start of the treatment with this drug)

• Dosing status of Xeljanz tablets

Using the SAS (including the subgroups by mean daily dose) and the set of patients treated for a long term (including the subgroups by mean daily dose), dosing data for this drug will be summarized with respect to the following aspects:

- Starting daily dose [5 mg, 10 mg, 15 mg, 20 mg, >20 mg]
- Duration of treatment [\leq 15 weeks, >15 to \leq 30 weeks, >30 to \leq 45 weeks, >45 to \leq 60 weeks, >60 to \leq 75 weeks, >75 to \leq 90 weeks, >90 to \leq 105 weeks, >105 to \leq 120 weeks, >120 to \leq 135 weeks, >135 weeks]
- Total duration of treatment (patient-years) [≤15 weeks, >15 to ≤30 weeks, >30 to ≤45 weeks, >45 to ≤60 weeks, >60 to ≤75 weeks, >75 to ≤90 weeks, >90 to ≤105 weeks, >105 to ≤120 weeks, >120 to ≤135 weeks, >135 weeks] (The total duration of treatment in each category and the accumulated total duration of treatment will be presented.)
- Mean daily dose by duration of treatment (mg) (summary statistics) [<15 mg, ≥15 mg] [<17 mg,
 ≥17 mg], with the following categories for the duration of treatment:
 - Any duration of treatment
 - Duration of treatment ≤15 weeks
 - Duration of treatment > 15 to ≤ 30 weeks
 - Duration of treatment >30 to <45 weeks

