- Malignancy
- Cardiovascular events (including lipids increased and hyperlipidaemia)
- Cardiovascular events (excluding lipids increased and hyperlipidaemia)
- Lipids increased and hyperlipidaemia
- Rhabdomyolysis and myopathy

In addition, patients who experienced adverse reactions in the scope of the safety specification will be summarized in terms of n and proportion by SOC and PT, for different kinds of action taken and outcome.

Timing of onset of elements in the safety specification

Patients who experienced adverse reactions of each element in the safety specification will be summarized by timing of first onset, in terms of n and proportion as well as incidence and its 95% CI. For the purpose of summarization by time to onset, the denominator to calculate the proportion will be the number of patients who took at least one dose during each time category, and the denominator to calculate the incidence will be the duration of exposure in each time category. The categories for onset timing will be given by $[\le 15 \text{ weeks}, > 15 \text{ to} \le 30 \text{ weeks}, > 30 \text{ to} \le 45 \text{ weeks}, > 45 \text{ to} \le 60 \text{ weeks}]$, except for malignancy, for which given by ≤ 15 weeks, ≥ 15 to ≤ 30 weeks, ≥ 30 to ≤ 45 weeks, ≥ 45 to ≤ 60 weeks, ≥ 60 to ≤ 75 weeks, >75 to ≤ 90 weeks, >90 to ≤ 105 weeks, >105 to ≤ 120 weeks, >120 to ≤ 135 weeks, >135 weeks].

Relationship between concomitant drugs and adverse reactions

To investigate the relationship between concomitant biologics/immunosuppressants or concomitant CYP3A4 inhibitors/CYP2C19 inhibitors and adverse reactions included in the scope of the safety specification, development of those adverse reactions will be summarized in patients with and without concomitant use of a biologic/immunosuppressant and in patients with and without concomitant use of a CYP3A4 inhibitor/CYP2C19 inhibitor, by PT in terms of number of patients. Concomitant drugs used after the first onset of a target event will be excluded from the summarization. Concomitant drugs considered in this investigation include:

- Biologics (including recombinants)/immunosuppressants: abatacept, adalimumab, anakinra, azathioprine, baminercept, canakinumab, certolizumab, certolizumab pegol, cyclosporine, efalizumab, etanercept, golimumab, infliximab, ofatumumab, rituximab, Syk kinase inhibitors, tacrolimus hydrate, tocilizumab, sarilumab, zanolimumab, vedolizumab, ustekinumab, secukinumab, ixekizumab, and 6-mercaptopurine

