- CYP3A4 inhibitors/CYP2C19 inhibitors: clarithromycin, telithromycin, nefazodone, itraconazole, ketoconazole, atazanavir, darunavir, indinavir, lopinavir, nelfinavir, ritonavir, saquinavir, tipranavir, tacrolimus hydrate, cyclosporine, amitriptyline, clomipramine, fluconazole, fluvoxamine, imipramine, ticlopidine, esomeprazole, fluoxetine, moclobemide, omeprazole, and voriconazole

• Adverse reactions in patients excluded from and included in the SAS

Adverse reactions occurring in CRF-collected patients who are excluded from the SAS will be listed in tabular form. In addition, adverse reactions occurring in patients included in the SAS and in patients excluded from the SAS will be summarized by SOC and PT in terms of n and proportion of patients.

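### The split by CYP3A4/CYP2C19 inhibitor use names no data source, and the only concomitant-drug record described can identify at most 2 of the 26 listed agents

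*SAP*

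**What the plan says.** SAP 8.2.3.1, under the relationship between concomitant drugs and adverse reactions, plans two splits of the safety-specification reactions: one by use of biologics or immunosuppressants, and one by use of CYP inhibitors. The second is a count "in patients with and without concomitant use of a CYP3A4 inhibitor/CYP2C19 inhibitor, by PT in terms of number of patients". The agents are listed by name, beginning "CYP3A4 inhibitors/CYP2C19 inhibitors: clarithromycin, telithromycin, nefazodone, itraconazole, ketoconazole". A timing rule applies: "Concomitant drugs used after the first onset of a target event will be excluded from the summarization". SAP 8.2.3.2 repeats both splits for adverse events with the same lists. Neither section names a CRF entry as the source of drug exposure.

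Protocol 7.3.4.1 describes the concomitant drug record. It covers treatments for ulcerative colitis, in four classes: "5-ASAs (oral, enema, suppository), steroids (oral, enema, suppository, injection), immunomodulators (oral, injection), biological products (injection").

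SAP 8.2.2 defines concomitant medications as drugs in the CRF entry "Drug therapies for UC prior treatment and concomitant therapies", used from the start of treatment to discontinuation or 60 weeks, whichever is earlier. It says the definition is aligned with the collection period for reactions and events "so that relationship to adverse reactions and AEs can be assessed".

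**The concern.** A with/without table presents its second column as unexposed patients. That is sound only if use of each listed drug was asked about in every patient. Most of the listed inhibitors are not UC treatments, and the documents describe no general medication record. If the table is built on the UC record, patients taking an unrecorded inhibitor fall into the 'without' column. The 'with' column would hold only patients on drugs that the SAP also counts as immunosuppressants.

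The stated purpose is to investigate how CYP inhibitors relate to safety-specification events. On that data base, neither a difference between the columns nor its absence would bear on the question, and a reader of the re-examination report would not learn this from the column labels.

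**Working it through.** The plan states no figure here. The check counts the SAP lists and matches them to the records described.

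**1. Count the lists (SAP 8.2.3.1; same in 8.2.3.2).**
- CYP3A4/CYP2C19 inhibitors: 26 distinct agents.
- Biologics/immunosuppressants: 25 entries.
- On both lists: 2 (tacrolimus hydrate, cyclosporine).
- On the CYP list only: 26 − 2 = 24. These are 2 antibiotics, 4 azole antifungals, 8 HIV protease inhibitors, 7 antidepressants, ticlopidine and 2 proton-pump inhibitors (2 + 4 + 8 + 7 + 1 + 2 = 24).

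**2. Match them to the UC drug record (protocol 7.3.4.1; SAP 8.2.2).**
- Tacrolimus: SAP 5.4.2 treats it as a UC therapy, so it can be identified.
- Cyclosporine: not named as a UC therapy, but the protocol does not restrict immunomodulators to named agents, so it can be identified if entered there.
- The other 24 belong to none of the four classes.
- Identifiable: at most 2/26 = 7.7%. No described field: 24/26 = 92.3%. If cyclosporine is not entered as a UC drug, these become 1/26 = 3.8% and 25/26 = 96.2%.

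These are shares of drug names, not of patients.

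**3. Look for another source covering all patients.**

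| Record | Scope | All-patient record of the 24 agents? |
|---|---|---|
| Protocol Table 2 | Concomitant-therapy row is for UC; no general medication row | No |
| Protocol 7.3.2, prior treatment | "The status of prior treatment (drug and non-drug therapy) for the last episode before commencement of XELJANZ treatment", plus past biologics | No |
| Protocol 7.3.5, vaccination | Herpes zoster vaccine, and "Pneumococcal vaccine: Status and date of vaccination" | No |
| Protocol 7.3.6, prophylaxis | Drug names, for tuberculosis, Pneumocystis pneumonia and hepatitis B only | No |
| Protocol 7.3.11, Intervention item | Only patients who had an adverse event; drug names not mentioned | No |
| Protocol 7.3.11, separate follow-up | Adverse reactions only, when the sponsor judges it necessary; drugs not mentioned | No |

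**4. What the two columns would then contain.**
- 'With' = tacrolimus or cyclosporine recorded for UC. Both (2 of 2) are on the immunosuppressant list, so every such patient is also in the immunosuppressant 'with' group.
- 'Without' = neither drug recorded for UC. Users of any of the other 24 agents are included and cannot be told apart.

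**The case against.** The strongest objection is that the CRF decides the matter and is a separate document (protocol section 14). It may hold a wider medication page. This stands. What the documents show is that the SAP names no source and that the only record described is too narrow. A reader might infer that the split is invalid outright, but that cannot be concluded without the CRF.

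Four further limits also stand:
- **The link to SAP 8.2.2 is inferred.** One might read 8.2.2 as choosing the UC entry for this table. Its purpose clause explains the time window, and 8.2.3.1 and 8.2.3.2 do not cite 8.2.2. Applying that definition here is reasonable but not stated.
- **The timing rule does not by itself exclude the Intervention item.** A drug given for an earlier, different event could precede the target event. Even so, the item exists only for patients with an event, so it cannot establish who was unexposed.
- **25 of 26 is not the fair lead.** The narrower reading of immunomodulators comes from an SAP label for prior treatment, not from what the protocol says is collected.
- **The output is modest.** It gives patient counts by preferred term, with no proportion, risk ratio, interval or test specified, and SAP 4.2 has no decision rule. A reader might infer a biased risk ratio of some known size. The table produces no such ratio, and the documents give no prevalence of inhibitor use from which to work one out.

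The missing-data rule in SAP section 7 does not rescue the split. It does not clearly reach a drug for which no item exists. If it did, patients with no recorded inhibitor would be unknown, which still leaves no 'without' group.

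**Conclusion.** Wrong as written, conditional on the CRF; minor. On the data the documents describe, the CYP split can identify at most 2 of 26 listed agents. Its 'with' group is contained in the immunosuppressant 'with' group, and its 'without' group is not an unexposed group. The result would be a mislabelled safety table, which is more than an omitted detail.

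This rests on two assumptions: that the CRF follows the protocol's description of concomitant drug collection, and that the UC drug record is the source intended for the table. The number of patients affected is unknown.

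The reach is limited to one secondary, count-only table, prepared once for adverse reactions and once for adverse events. It is tempting to extend the criticism to the whole concomitant-drug analysis. The documents do not support that: the biologic/immunosuppressant split is not shown to be affected, and neither are the primary safety and effectiveness items.

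**What to change.** Check the CRF first, then amend SAP 8.2.3.1 and 8.2.3.2 in the same way.

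- **If the CRF records non-UC concomitant drugs for all patients:** name that record as the data source for the CYP split and keep the table.
- **If it does not:** relabel the split as 'recorded concomitant tacrolimus/cyclosporine for UC (yes/no)', present no 'without CYP inhibitor' group, and state that the other listed inhibitors were not collected.

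The cost is SAP wording only. The investigation period was planned to end in June 2021 and SAP 4.0 is dated 30 May 2022, so the choice turns on data already held. The downside of the second route is that one secondary descriptive table, in its reaction and event forms, is narrowed and no longer addresses CYP inhibition in general.

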7.5.2. Rationale for sample size

Based on the results of clinical studies conducted up to approval, the incidence of herpes zoster in Japanese patients with ulcerative colitis chronically treated with XELJANZ was higher than that in the overall population of the studies. Therefore, on the assumption that the true incidence of herpes zoster in Japanese patients with ulcerative colitis is 8/100 person-years, the sample size will be 470 when the probability of the lower limit of 95% confidence interval for the incidence of herpes zoster not falling below 4/100 person-years (results for the overall population of the studies) is 80%.

*: If it is assumed that 5% of the registered patients are unevaluable for the safety due to failure to show up or other reasons, 495 patients need to be registered to ensure that 470 patients are included in the safety analysis set.

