8.2.3. Safety analyses

Adverse reactions or AEs included in a summarization will be those that developed from the start of treatment to the end of the observation period or 60 weeks after the start of treatment, whichever came first, except for malignancy, for which all events occurring by the end of observation period will be included in a summarization. All adverse reactions and AEs reported in this study will be included in a listing.

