To evaluate the dose-response relationship concerning the safety of the treatment with this drug, the following analyses will be performed in the patients treated at a higher dose level defined in Section 5.4.1 and in the patients treated at a lower dose level. To eliminate the effect of including patients who discontinued treatment during the induction phase, similar analyses will also be performed in patients treated at a higher dose level for a long term and in patients treated at a lower dose level for a long term:

• Adverse reactions of each element in the safety specification will be summarized in terms of number and proportion of patients as well as incidence and its 95% CI. In addition, the risk ratio and risk difference with their 95% CI will be presented for the patients treated at a higher dose level compared with those at a lower dose level.

• Adverse reactions will be summarized by SOC and PT in terms of number and proportion of patients.

In addition, to investigate the temporal change in the risk of the occurrence of each event, the following analyses will be performed in the patients treated at a higher dose level and patients treated at a lower dose level:

[figure not shown]
- Patients who experienced adverse reactions of each element in the safety specification will be summarized by timing of first onset, in terms of n and proportion as well as incidence and its 95% CI. As for the denominator to calculate the proportion, the denominator to calculate the incidence, and the categories used for onset timing, the corresponding descriptions in (1) should be followed.
- A Kaplan-Meier plot will be presented for the time to first onset of any adverse reaction included in each element in the safety specification.

• Subgroup analyses regarding patient characteristics

According to Section 8.1.3, the risk ratio based on the proportion of patients who experienced adverse reactions of each element in the safety specification will be determined and graphically presented for different subgroups regarding each of the patient factors defined in Section 8.2.2 in which events developed in ≥ 10 patients. Risk ratios will not be calculated for subgroups in which events developed in < 10 patients.

For each relevant subgroup defined in Section 5.4.2, patients who experienced adverse reactions will be summarized by SOC and PT in terms of n and proportion.

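### The concomitant-drug tables give only counts of event patients and set no exposure rule for event-free patients, so they cannot show a drug–event relationship; any risk ratio formed from them is pulled downward to the extent that drugs are started after Day 1

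*SAP*

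**What the plan says.** SAP 8.2.3.1 (adverse reactions) and 8.2.3.2 (adverse events) each contain an item on concomitant drugs. Its stated purpose is to investigate how biologics/immunosuppressants, or CYP3A4/CYP2C19 inhibitors, relate to events in the safety specification. Patients with and without use are tabulated "by PT in terms of number of patients". No other statistic is named, although neighbouring items ask for proportions or for incidence with its 95% CI.

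One exposure rule is given in both sections: "Concomitant drugs used after the first onset of a target event will be excluded from the summarization".

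The only general definition of concomitant medication is in SAP 8.2.2. It counts drugs used from the start of treatment "to the discontinuation of treatment or 60 weeks after the start of treatment, whichever came first", a window chosen "so that relationship to adverse reactions and AEs can be assessed".

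Two other places bear on the point. SAP 8.2.3.3 plans "the risk ratio based on the proportion of patients who experienced adverse reactions of each element in the safety specification" by the patient factors of 8.2.2, where events occurred in at least 10 patients. The SAP Appendix 2 example table has a mock row for concomitant use of a drug, with n/N, risk ratio and CI. Neither place mentions the two drug classes or the first-onset cut.

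**The concern.** There are two gaps.

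First, a count of event patients with use and a count without use say nothing about a relationship unless one knows how many patients, or how much time, stood behind each count. This needs no assumption.

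Second, the denominators the SAP would supply do not match the numerators. A patient with an event is a user only if the drug came before onset. A patient without one is, by the 8.2.2 definition, a user if the drug was taken at any time before discontinuation or Week 60. Event-free patients therefore have longer to become users. This is the familiar immortal-time problem, and it lowers the apparent risk in users.

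Serious infections and herpes zoster are important identified risks, and whether added immunosuppression raises them is the question these tables are meant to answer. The final analysis supports the re-examination application. A ratio formed from these tables could hide a real increase.

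**Working it through.** The plan states no figure for this analysis, so there is none to reproduce. The nearest is the mock row in Appendix 2: (9/798)/(12/2521) = 2.37, with log standard error √(1/9 − 1/798 + 1/12 − 1/2521) = 0.439 and 95% CI 1.00–5.60, as printed. It shows the form a concomitant-drug ratio would take: patients over patients, with no person-time.

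**Inputs**
- From the documents: follow-up is capped at 60 weeks, T = 60 × 7/365.25 = 1.150 years. The event rate λ is 0.08 per year, from protocol 7.5.2 ("true incidence of herpes zoster in Japanese patients with ulcerative colitis is 8/100 person-years"). The planned safety set is 470.
- Assumed, not in the documents: a higher event rate of 0.20; new starts of the concomitant drug σ = 0.3 or 0.6 per year; discontinuation δ = 0.6 per year; a share b of all patients already on the drug at Day 1. Times are exponential and the drug has no effect.

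**Formulas**, with A = λ + δ + σ:
- event patients: C = λ/(λ+δ) × (1 − e^(−(λ+δ)T))
- event patients without prior use: N = (1−b) × λ/A × (1 − e^(−AT))
- users as the SAP would class them: U = b + (1−b) × σ/A × (1 − e^(−AT))
- risk ratio = [(C − N)/U] / [N/(1 − U)]

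**One case in full** (λ = 0.08, σ = 0.3, δ = 0.6, b = 0)
- A = 0.98 and 1 − e^(−0.98 × 1.150) = 0.6760, so U = 0.2069 and N = 0.0552.
- 1 − e^(−0.68 × 1.150) = 0.5425, so C = 0.0638 and C − N = 0.0086.
- Risk ratio = (0.0086/0.2069)/(0.0552/0.7931) = 0.60, when the truth is 1.
- Users are 0.0086/0.0638 = 13% of event patients, but (0.2069 − 0.0086)/(1 − 0.0638) = 21% of event-free patients.

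In 470 patients this is about 4 event patients with use and 26 without. The SAP table would stop there. Set against 97 users and 373 non-users, the two counts give the ratio of 0.60.

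**Splitting person-time at drug start, same case.** Unexposed time per patient is 0.6760/0.98 = 0.690 years. Total time is 0.5425/0.68 = 0.798 years, so exposed time is 0.108 years. The rates are 0.0552/0.690 = 0.080 and 0.0086/0.108 = 0.080, a rate ratio of 1.00.

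**All cases: risk ratio when the truth is 1**

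| On drug at Day 1 (b) | λ 0.08, σ 0.3 | λ 0.08, σ 0.6 | λ 0.20, σ 0.3 | λ 0.20, σ 0.6 |
|---|---|---|---|---|
| none | 0.60 | 0.58 | 0.63 | 0.60 |
| 10% of patients | 0.71 | 0.64 | 0.73 | 0.67 |
| 20% of patients | 0.77 | 0.69 | 0.79 | 0.71 |
| all users (σ = 0) | 1.00 | 1.00 | 1.00 | 1.00 |

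Simulation of the first row gives 0.57–0.63, the same within simulation error.

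**Sensitivity to the start pattern.** Suppose instead that 30% of patients ever use the drug, that new starts are uniform over 60 weeks and that λ = 0.08. With no discontinuation (with 0.6 per year in brackets), the simulated risk ratio is 0.79 (0.87) if two thirds of users are on it at Day 1, 0.69 (0.81) if half are, 0.43 (0.57) if none are, and 1.00 if all are.

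**A true hazard ratio of 2**, under the rates of the table, appears as 1.12–1.17 if nobody is on the drug at Day 1 and as roughly 1.2–1.5 if 10–20% of patients are. The person-time split returns about 2.0.

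**The case against.** The strongest objection is that the item plans no ratio. A count of event patients who did or did not use a drug before onset is not biased in itself; bias enters only when someone divides by ever-user totals. This stands. A reader might infer that the SAP analysis is biased toward safety as written, and the documents do not support that. Appendix 2 shows that a concomitant-drug risk ratio is contemplated in some form, but the SAP does not tie it to these drug classes or to the first-onset cut.

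A reader might also infer that the bias is certain. It is not: drugs already in use at Day 1 contribute none. SAP 8.2.2 counts any drug used from treatment start and draws prior and concomitant therapy from the same CRF entry, so carry-over use is plausible. The share is not stated.

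Nor is the first-onset exclusion the fault. It keeps out drugs given after, and perhaps because of, the event. Without it, under no effect at 8/100 person-years and with discontinuation at 0.6 per year, the ratio errs upward, to 1.08–1.30 when some or all users start after Day 1. Nor does the event-free window always run to 60 weeks; it ends at discontinuation if that is earlier, and it has to be inferred from 8.2.2.

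Finally, this is a descriptive secondary table with no decision rule, and the primary safety items are untouched. That limits the weight of the point. It does not give the table a denominator.

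**Conclusion.** The point holds in this form. The tables in 8.2.3.1 and 8.2.3.2 cannot show the relationship they set out to investigate, because they hold counts without denominators or person-time. That part rests on the text alone.

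The second part is conditional. If the counts are set against totals with and without use, the windows are unequal and the ratio is too low to the extent that drugs are started after Day 1. Under no effect it is about 0.57–0.63 with nobody on the drug at Day 1, 0.64–0.79 with 10–20% of patients on it, and 1.00 when all users are. These figures rest on assumed start and discontinuation rates, and the documents do not say where in this range the study lies. The change is worth making, because the split analysis removes the dependence on that unknown share.

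**What to change.** In 8.2.3.1 and 8.2.3.2:

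- Keep the exclusion of drugs used after first onset.
- For biologics and immunosuppressants given for ulcerative colitis, split each patient's event-free exposure at first concomitant use. Protocol 7.3.4.1 collects duration of treatment for these drugs.
- Report events, person-years and incidence with the 8.1.4 CI for exposed and unexposed time, and their rate ratio with 95% CI.
- Do this per safety-specification element rather than per preferred term, and give the ratio only where events occurred in at least 10 patients, as in 8.2.3.3.
- For CYP3A4/CYP2C19 inhibitors, state that the analysis is limited to drugs with recorded dates. Protocol 7.3.4.1 collects ulcerative colitis therapies only, so most of the listed inhibitors have no stated source of dates.
- Say how a drug started before and continued after onset is classed. Also say how malignancy is handled: its events are counted without the 60-week cap ("except for malignancy, for which all events occurring by the end of observation period will be included in a summarization"), while the 8.2.2 drug window stops at Week 60 at the latest.

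The cost is SAP wording in two sections and modest programming, with no new data. The drawback is wide intervals. In the worked case, about 4 exposed and 26 unexposed events give a log standard error of √(1/4.1 + 1/25.9) = 0.53, so a rate ratio of 1 would carry a 95% CI of about 0.35–2.8.
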